3.2 Sample size justification

The sample size of the full phase 2/3 study is calculated based on data from clinical experience and on Sponsor expectations as reported in Table 2:

Table 2: Assumptions for primary endpoints

Primary endpoint*	Standard of care (control)	Reparixin
Time to primary endpoint of phase 2	2 days	5 days
Time to primary endpoint of phase 3	2-4 days	4-8 days

* see section 3.5.1.

Based on the following assumptions:

- an enrollment phase of 2 months,

- a total follow-up of 21 days,
- a randomization ratio (reparixin:control) of 2:1
- an exponential distribution for survival probability $S(t) = e^{-\lambda t}$,
- a comparison between treatment by means of a log-rank test,
- an interim analysis framework as described in section 4.5, and
- a correction of the type I and II errors by means of O'Brien-Fleming spending functions

a total of 109 events (corresponding to approximately 111 subjects) will allow to provide >80% power to show superiority of reparixin vs standard of care in terms of primary endpoint of phase 3, controlling the type I error under 0.025.

Based on the same assumptions reported above, phase 2 portion of the study will be performed when a total of 46 events (corresponding to approximately 48 subjects) has happened. This allow to achieve approximately 80% power to show superiority of reparixin vs standard of care in terms of (not severe) primary endpoint of phase 2, controlling the type I error under 0.025.

The remaining portion of the 111 patients will be enrolled in the phase 3 study segment. Anyhow, due to the novel nature of the COVID-19 pandemic and being the primary efficacy endpoint planned in phase 3 not well established, it may require confirmation based on phase 2 data. For this reason, at the end of the phase 2 portion, power calculations may be reassessed, and sample size may be re-estimated for phase 3.

The adaptive design allows for the assessment of efficacy endpoint in phase 2 which are then seamlessly confirmed in the phase 3. Since primary endpoint of phase 3 will be tested only if superiority of reparixin is shown in phase 2 (at interim or final stage), the overall type I error of the study will be controlled at 0.025 via the hierarchical testing procedure.

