# 9 STATISTICAL CONSIDERATIONS

#### 9.1 Sample size

The sample size for this trial will be adaptively determined through a phase 2/3 design. Enrollment is planned to last approximately 2 months. Each patient will be randomly allocated to Reparixin or Control according to a randomization ratio of 2:1 and he/she will be followed for the entire treatment and follow-up duration for collecting the efficacy endpoints of each study phase.

For the Phase 2 portion of the study, the primary analysis will compare Reparixin versus Control in terms of time to a composite endpoint (primary endpoint of phase 2) including the following events: requirement of supplemental oxygen treatment, mechanical ventilation use, admission to ICU, and any requirement of rescue medication. Based on clinical experience, an improvement of the median time freedom from composite event of 1.5 times is expected. Assuming an exponential distribution, a total sample size of 48 patients will allow to provide 80% power to show superiority of Reparixin compared to control using a log-rank test at a one-sided significance level of 0.025.

The sample size for the phase 3 is based on assessment of superiority of Reparixin compared to control arm in terms of freedom from a composite endpoint (primary endpoint of phase 3) of severe events including death, admission to the ICU, requirement of mechanical ventilation.

Based on same assumptions of phase 2 regarding randomization (2:1) and expecting to double the median time freedom from severe composite event using Reparixin compared to control (from 2-4 to 4-8 days), a total sample size of 111 patients will allow to achieve a power of 90% to show superiority of Reparixin over control using a log-rank test at a one-sided significance level of 0.025. No drop-out are expected to happen. The number of patients to be included may be revised based on considerations from Phase 2 data analysis.

Primary endpoint of phase 3 will be tested only if superiority of Reparixin is shown in phase 2. Thus, the overall type I error of the study will be controlled at 0.025 via the hierarchical testing procedure.

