### **11.2** Schedule of Evaluations

The following schedule reports the relative timeframes and all the evaluations and assessments that are performed during the study:

Study procedures	Screening	Baseline	Day 1	Day 2	Week 1	End of treatment	End of follow up
Informed Consent	Х						-
Inclusion/Exclusion Criteria	X	Х					
Pregnancy Test	X						Х
Randomization		Х					
Demographics	Х						
Medical History	X						
Previous And							
Concomitant	Х	X	Х	Х	Х	Х	Х
Medications							
Clinical severity	X	X	Х	X	X	Х	Х
score	Λ	Λ	Λ	Λ	Λ	Λ	Λ
Liker scale	Х	Х	Х	Х	Х	Х	Х
Dyspnea VAS scale	Х	Х	Х	Х	Х	Х	Х
Body temperature	Х	Х	Х	Х	Х	Х	Х
Hematology	V	X	$\mathbf{v}$	v	X	V	Х
evaluations*	Х	л	Х	X	Λ	Х	Λ
Oxigen treatment	X	X	Х	X	X	Х	Х
(time and quantity)	Λ	Λ	Λ	Λ	Λ	Λ	Λ
Mechanical	Х	X	Х	Х	Х	Х	Х
ventilation (Yes/No)	Λ	Λ	Λ	Λ	Λ	Λ	Λ
ICU admission	Х	X	Х	Х	Х	Х	Х
(Yes/no)	Λ	Λ	Λ	Λ	Λ	Λ	Λ
Chest radiologic	Х	X§	X§	X§	X§	Х	X§
imaging	Λ	$\Lambda^{\circ}$	$\Lambda^{\mathfrak{g}}$	$\Lambda^{\circ}$	$\Lambda^{\circ}$	Λ	$\Lambda^{\circ}$
PaO2, SpO2, FiO2	Х	Х	Х	Х	Х	Х	Х
CRP, Hs-CRP	Х	Х	Х	Х	Х	Х	Х
Cytokine profile **	Х	Х	Х	Х	Х	Х	Х
Reparixin blood			$\mathbf{v}$	v	v	V	V
concentration **			Х	Х	Х	Х	Х
SARS-CoV-2		v			v	V	V
virologic counts **		X			Х	Х	Х
Study drug		X					
dispensation		Λ					
Verify study							
medication dosing			Х	X	Х	Х	
compliance							
Record AEs / SAEs	Х	Х	Х	Х	Х	Х	Х

\* Including routine hematology as for local laboratory procedures and predefined hematochemical evaluations required for this study; \*\* Not mandatory; § When deemed appropriate by the investigators.

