3.1 Visit Schedule and Visit Windows

Assessments and study visits will be performed as listed in Table 1. Paragraph no. 7 “Assessments and procedures” of Study Protocol contains additional details about scheduled visits, evaluations and assessments that are performed during the study.

Baseline is defined as the last visit prior to randomization. Unless otherwise specified, baseline values are defined as the measurements taken during this visit.

Table 1: Schedule of evaluations

Study procedures	Screening	Baseline	Day 1	Day 2	Week 1	End of treatment	End of follow up
Informed Consent	X						
Inclusion/Exclusion Criteria	X	X					
Pregnancy Test	X						X
Randomization		X					
Demographics	X						
Medical History	X						
Previous And Concomitant Medications	X	X	X	X	X	X	X
Clinical severity score	X	X	X	X	X	X	X
Liker scale	X	X	X	X	X	X	X
Dyspnea VAS scale	X	X	X	X	X	X	X
Body temperature	X	X	X	X	X	X	X
Hematology evaluations*	X	X	X	X	X	X	X
Oxygen treatment (time and quantity)	X	X	X	X	X	X	X
Mechanical ventilation (Yes/No)	X	X	X	X	X	X	X
ICU admission (Yes/no)	X	X	X	X	X	X	X
Chest radiologic imaging	X	X§	X§	X§	X§	X	X§
PaO ₂ , SpO ₂ , FiO ₂	X	X	X	X	X	X	X
CRP, Hs-CRP	X	X	X	X	X	X	X
Cytokine profile **	X	X	X	X	X	X	X
Reparixin blood concentration **			X	X	X	X	X
SARS-CoV-2 virologic counts **		X			X	X	X
Study drug dispensation		X					
Verify study medication dosing compliance			X	X	X	X	
Record AEs / SAEs	X	X	X	X	X	X	X

* Including routine hematology as for local laboratory procedures and predefined hematochemical evaluations required for this study;

** Not mandatory; § When deemed appropriate by the investigators.

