7.1.2 Analysis details

The composite endpoints for phase 2 and phase 3 (section 3.5.1) will be summarized along with their single component by a binomial response rate at each time point (only the first event will be considered). The Clopper-Pearson method will be used to estimate the two-sided 95% CIs.

Primary analyses on time to composite endpoint(s) will be performed using the KM methodology and the one-

sided log-rank test will be used to test for differences between treatment groups. See section 4.1 for more details on time-to-event analysis and representation.

The primary endpoint of phase 2 will be assessed also in phase 3 as secondary analysis, and vice versa.

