Composite endpoint of phase 2 and Time to event (days)	
From ADDITIONAL INFORMATION form:
 
 • if “Has the patient been admitted to the ICU?” = “Yes”, then component1 = “Yes” and date of event1 = Date of Visit • if “Has the patient been admitted to the ICU?” = “No”, then component1 = “No” 
From PATIENT STATUS form:
 
 • if “Is the subject eligible to switch to rescue medication?” = “Yes”, then component2 = “Yes” and date of event2 = Rescue treatment start date 
 ○ If Rescue treatment start date is missing, then Date of Visit will be used • if “Is the subject eligible to switch to rescue medication?” = “No”, then component2 = “No” 
From ADDITIONAL INFORMATION and MECHANICAL VENTILATION forms:
 
 • If “Has the patient been mechanically ventilated?” = “Yes” and type = “Invasive mechanical ventilation”, then component3 = “Yes” and date of event3 = mechanical ventilation start date 
 ○ If mechanical ventilation start date is missing, then Date of Visit will be used • If “Has the patient been mechanically ventilated?” is not empty and type ≠ “Invasive mechanical ventilation”, then component3 = “No” 
From “Worsening based on PaO₂/FiO₂” (see above):
 
 • if a patient is classified as “Worsened”, then component4 = “Yes” and date of event4 = Date of Visit • if a patient is classified as not “Worsened” (excluding missing classification), then component4 = “No” 
The composite endpoint is equal to “Yes” if at least one post-baseline component (1-4) is equal to “Yes” and the date of event is the corresponding date of event. In case of more component equal to “Yes”, the first date will be used.
 
Otherwise, if all component (1-4) are equal to “No” the composite endpoint will set as “No”. The date of event will be last date where is known that all components are equal to “No”.
 
Time to composite endpoint (days) = Date of event - Date of randomization

Parameter	Derivation

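### The phase 2 power of about 80% assumes exactly timed events, but the PaO2/FiO2 component is dated at sparse visits; allowing for that, power is about 68-76% if a quarter or more of first events are visit-dated

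*SAP*

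**What the plan says.** - **Power.** SAP 3.2, Table 2 gives the assumed times as "Time to primary endpoint of phase 2 2 days 5 days" (control, then reparixin). With an exponential distribution, 2:1 allocation, 21 days of follow-up and 46 events, it concludes: "This allow to achieve approximately 80% power to show superiority of reparixin vs standard of care in terms of (not severe) primary endpoint". It makes no allowance for how events are detected.
- **Schedule.** SAP 3.1 states: "Assessments and study visits will be performed as listed in Table 1". In that table, and in protocol 11.2, the row "PaO2, SpO2, FiO2" is marked after baseline at Day 1, Day 2, Week 1, end of treatment and end of follow-up only.
- **Dating.** SAP 9.1, Table 7 defines the oxygen component (component 4) as a fall in PaO2/FiO2 of at least one third from baseline, "and date of event4 = Date of Visit". ICU admission is also dated at the visit in the composite. Rescue treatment and invasive ventilation carry their own start dates.
- **Analysis.** SAP 4.1 and 7.1.2 plan Kaplan-Meier estimates and a one-sided log-rank test. No interval-censored or discrete-time method is planned.

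**The concern.** The plan sets out to separate 2 days from 5 days, yet it schedules no PaO2/FiO2 between day 2 and day 7. A patient whose ratio falls on day 3 and one whose ratio falls on day 6 are both recorded as day 7 events. The log-rank test then sees a tie where the arms are expected to differ, so information is lost that the sample size calculation counted on.

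This matters because phase 2 is a gate. The phase 3 endpoint is tested only if phase 2 shows superiority, and SAP 7.1.3.1 bases the decision to proceed on the primary analysis alone. An overstated power understates the chance that an effective treatment stops here.

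**Working it through.** **Inputs.** From SAP 3.2: 46 events, 48 subjects (32 vs 16), 2 vs 5 days, exponential times, two months of enrolment, 21 days of follow-up. From SAP Table 4: interim at 23 events, efficacy p < 0.00258, futility p ≥ 0.23349, final p < 0.024. Protocol 9.1 gives the level: "using a log-rank test at a one-sided significance level of 0.025". The 2 and 5 days are read as medians; Table 2 does not label them.

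**Step 1: reproduce the stated figure with exact dates.**
- Hazard ratio = 2/5 = 0.40.
- Expected events by day 21 = 16 × (1 − 2^(−21/2)) + 32 × (1 − 2^(−21/5)) = 16.0 + 30.3 ≈ 46.2, matching the stated 46.
- Schoenfeld drift = √(46 × 2/3 × 1/3) × ln 2.5 = 3.197 × 0.916 = 2.930. Fixed-design power = Φ(2.930 − 1.960) = 83.4%.
- The two-stage calculation at information fraction 0.5 with the Table 4 boundaries gives 83.1% ignoring futility and 80.1% with futility applied. Simulation gives 80.0%.

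The SAP figure is therefore correct for exactly timed events.

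**Step 2: how much of the information falls in the gap.** Probability of a first event between days 2 and 7:
- reparixin: 2^(−2/5) − 2^(−7/5) = 0.758 − 0.379 = 38%
- control: 2^(−2/2) − 2^(−7/2) = 0.500 − 0.088 = 41%

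**Step 3: simulate visit-based dating.** Each trial has 32 vs 16 patients, the interim at the 23rd recorded event, the Table 4 boundaries with futility applied, and a log-rank test with ties. A given share of first events is moved to the next visit and the rest are dated to the day. The documents fix neither the share nor the end-of-treatment day (7 days of treatment, extendable to 21), so both are varied.

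| Share visit-dated | Visits 1, 2, 7, 21 | Visits 1, 2, 7, 14, 21 | End of treatment spread over days 8-21 |
|---|---|---|---|
| 25% | 72.7% | 76% | 76% |
| 50% | 69.4% | 73% | 71% |
| 75% | 68.1% | 71% | not run |
| 100% | 70.1% | 72.7% | 72% |

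At a 10% share, power is about 77%. With daily dating through day 21 it is 79.3%. Repeat runs differ by one or two points.

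**Step 4: further checks.**
- Ignoring futility, which the protocol calls nonbinding: 83.0% with exact dates against 72.1% with all events dated at days 1, 2, 7 and 21. The loss is about the same.
- Futility stop under the planned effect: 9% with exact dates, rising to 10-13%.
- Type I error under a common schedule: about 0.023 simulated.
- Reading 2 and 5 days as means: 79.0% with exact dates, 68.9% with all events dated at days 1, 2, 7 and 21.
- Daily readings to day 7, then day 21: 74.7% (76.4% if the times are means).

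**The case against.** **The gap concerns one component.** A reader might infer that no event between days 2 and 7 can be timed. The documents do not support that. Rescue and invasive ventilation have start dates, and Table 7 uses an ICU admission date for other variables, so that date is evidently collected. Only a PaO2/FiO2 fall has no alternative date.

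**The share is unknown.** A reader might also infer that PaO2/FiO2 drives the endpoint and that power is simply 70%. No section says how many first events come from this component. The loss is a range: about 3 points at a 10% share (80 − 77) and 4 to 12 points at shares of 25-100% (80 − 76 to 80 − 68). This objection stands, and it is why the result is conditional.

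**Visit-based assessment is a common design choice, and validity is intact.** This also stands. With the same schedule in both arms the test is not inflated, so the issue is efficiency and an inaccurate power statement, not bias.

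**Denser sampling carries its own risk.** In an open-label trial, taking the worst charted value would let the number of readings differ between arms. It would also capture transient falls and so change the endpoint. This rules out a worst-value rule, but not one pre-specified daily reading on the same schedule in both arms.

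**Local data may exist.** Protocol 7.2 and 7.4 leave measurements to local procedures and do not say whether daily gases are taken. Dated values may be available, but the derivation in Table 7 makes no use of them.

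**Conclusion.** The concern holds in limited form. The approximately 80% in SAP 3.2 is correct only for exactly timed events. Under the SAP's own schedule and dating rule, phase 2 power is about 68-76% if 25-100% of first events are visit-dated, and about 77% if 10% are.

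This rests on 2 versus 5 days read as medians, futility applied, an assumed end-of-treatment day, and falls that persist to the next visit. Falls that recover between visits would be missed; this is not modelled.

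It would be wrong to carry the reduced figure into protocol 9.1. That section assumes a 1.5-fold median, for which 46 events give Φ(3.197 × ln 1.5 − 1.960) = Φ(−0.664), or about 25% power. That is a separate and larger inconsistency. Severity: should be fixed; it does not invalidate the test.

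**What to change.** 1. **SAP 3.2 only:** restate phase 2 power as a conditional range of about 70-75% that allows for visit-based dating, naming the assumed visit-dated share and end-of-treatment day. This costs nothing beyond the text change.
2. **SAP 9.1, Table 7:** date ICU events in the composite at the ICU admission date already used elsewhere in that table. This is a programming change.
3. **Where dated gas values are available:** record one pre-specified PaO2/FiO2 reading per day, on the same schedule in both arms, through day 21, and date component 4 at the measurement. This would restore about 79-80%. Stopping at day 7 recovers only about 75-77%. The cost is a CRF change and extra transcription. Do not use the worst charted value.
4. **Separately:** reconcile the 1.5-fold effect in protocol 9.1 with the 2 and 5 days in SAP Table 2. Do not relabel the protocol's power as 70-73%.

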# **5 POPULATION**

#### 5.1 Number of patients

A maximum of 48 patients with moderate-to-severe COVID-19 pneumonia will be enrolled in the Phase 2 study. Enrollment can be interrupted at any given time for futility or clear superiority reasons of the oral tablet vs IV infusion, or both vs standard of care, to proceed into Phase 3 or interrupt the clinical study.

The estimated number of 111 patients to be enrolled until the end of Phase 3 will be re-estimated based on the Phase 2 results.

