3.3 Randomization and blinding

Eligible subjects will be randomized in a 2:1 fashion to either reparixin or standard of care through an Interactive Response System (IRS).

Randomization will be stratified by site to ensure balanced assignment across treatment groups. A stratified permuted block randomization list will be generated with a computer procedure, randomizing an excess of subjects to allow competitive recruitment within each center. Each randomized subject will be allocated with randomization number according to the stratified randomization list.

Given the open-label nature of the trial and the stratification by site, random block sizes will be adopted in the randomization list to avoid that treatment assignments might be forecasted by investigators.

The master randomization list will be kept confidential and will not be disclosed to any other person than those for which is strictly required (i.e. independent statistician who create the list, and IRS provider personnel).

Mis-randomization events will be recorded as major deviation and reported in the final study report.

Randomization codes will not be reused in case of subject's dropouts.

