4.5 Interim analyses

Interim analyses are planned at specific time point during phase 2 and phase 3 for identification of early superiority of reparixin (efficacy) or for early stop of the trial for futility.

O'Brien-Fleming spending functions will be used to control the type I and II errors for analyses of primary endpoints. P-values boundaries for efficacy and futility at interim and final analyses for phase 2 and phase 3 are reported in Table 4 and Table 5, respectively.

Table 4: O'Brien-Fleming spending functions boundaries for primary analysis in phase 2

Analysis	Sample Size	Boundaries for primary endpoint	
		Efficacy	Futility
Interim #1	~27 (23 events)	p-value < 0.00258	p-value ≥ 0.23349
Final	48 (46 events)	p-value < 0.02400	p-value ≥ 0.02400

Table 5: O'Brien-Fleming spending functions boundaries for primary analysis in phase 3

Analysis	Sample Size	Boundaries for primary endpoint	
		Efficacy	Futility
Interim #1	~60 (60 events)	p-value < 0.00296	p-value ≥ 0.26674
Interim #2	~81 (81 events)	p-value < 0.00892	p-value ≥ 0.09841
Final	111 (109 events)	p-value < 0.02151	p-value ≥ 0.02151

The interim analyses will be conducted by DMC who will communicate to the Sponsor the result of the interim analysis and the consequent decision on the continuation of the study.

The following scenarios may emerge from the interim analysis:

- the communication from the DMC to the Sponsor will be "Not enough evidence for demonstrate superiority of reparixin". Since results are not considered enough to draw conclusions on primary

endpoints, the study enrolment will continue up to the next analysis step, and treatments and follow-ups will proceed without modifications.

- the communication from the DMC to the Sponsor will be “Superiority of reparixin is shown”. In this case, the following action will be taken according to the study phase:
 - Phase 2:
 - enrollment of subjects in phase 2 is stopped
 - already enrolled subjects continue their residual treatment and follow-up as planned
 - adaptation of phase 3, if needed;
 - enrollment of subjects in phase 3 may start;
 - Phase 3:
 - enrollment of subjects is stopped
 - already enrolled subjects continue their residual treatment and follow-up as planned
 - when last enrolled subject completes the follow-up and database is close, final analysis is performed and clinical study report will be released.

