7.1 Analysis of primary efficacy endpoints

7.1.1 Testing strategy and multiplicity adjustment

7.1.1.1 Phase 2

The following null hypothesis is defined: the freedom from composite endpoint (section 3.5.1) in reparixin is lower or equal than control:

$$H_0: T_{\text{REPARIXIN}} \leq T_{\text{CONTROL}}$$

$$H_1: T_{\text{REPARIXIN}} > T_{\text{CONTROL}}$$

where $T_{\text{REPARIXIN}}$ and T_{CONTROL} are the freedoms from composite endpoint for reparixin and standard of care, respectively. The null hypothesis H_0 will be rejected, and preliminary (to be confirmed in phase 3) superiority of reparixin shown if log-rank p-value will be lower than pre-specified threshold, depending at which analysis (interim or final) the test is performed. Thresholds are calculated according to O'Brien-Fleming spending function boundaries and are reported in Table 4.

7.1.1.2 Phase 3

The following null hypothesis is defined: that the freedom from severe composite endpoint (section 3.5.1) in reparixin is lower or equal than control:

$$H_0: \Pi_{\text{REPARIXIN}} \leq \Pi_{\text{CONTROL}}$$

$$H_1: \Pi_{\text{REPARIXIN}} > \Pi_{\text{CONTROL}}$$

where $\Pi_{\text{REPARIXIN}}$ and Π_{CONTROL} are the freedoms from severe composite endpoint for reparixin and standard of care, respectively. The null hypothesis will be rejected, and superiority of reparixin concluded if log-rank p-value will be lower than pre-specified threshold, depending at which analysis (first or second interim or final) the test is performed. Thresholds are calculated according to O'Brien-Fleming spending function boundaries and are reported in Table 5.

Phase 3 null and alternative hypotheses will be tested only if superiority of reparixin is shown in phase 2. Null hypotheses of both phases must be rejected in order to claim superiority of reparixin over standard of care. Consequently, no multiplicity correction of type I error will be applied on primary analyses.

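### Phase 2 type I error is stated as under 0.025, but the large-sample one-sided log-rank test with the Table 4 bounds gives about 0.028 to 0.035 at 32 versus 16 patients

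*SAP*

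**What the plan says.** SAP 3.2 plans 46 events in about 48 subjects, allocated 2:1, with about 80% power for the "not severe) primary endpoint of phase 2, controlling the type I error under 0.025". The same section makes the matching claim for 109 events in about 111 subjects: "primary endpoint of phase 3, controlling the type I error under 0.025".

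Table 4 in SAP 4.5 sets the interim efficacy bound at "p-value < 0.00258" with 23 events (about 27 patients) and the final bound at 0.02400 with 46 events. SAP 7.1.2 names a one-sided test: "sided log-rank test will be used to test for differences between treatment groups". Neither document names an exact, permutation or other small-sample version, or checks the error rate at this sample size.

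Table 7 in SAP 9.1 sets the time scale: "Time to composite endpoint (days) = Date of event - Date of randomization". ICU admission and PaO2/FiO2 worsening take the visit date. Rescue medication and invasive ventilation take their start dates. Protocol 9.4.5 makes the futility bound non-binding.

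On the overall claim, SAP 7.1.1.2 states: "Null hypotheses of both phases must be rejected in order to claim superiority of reparixin over standard of care".

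**The concern.** The bounds come from normal theory and use up the whole 0.025, so any skewness in the tested tail breaks the stated limit. There are 16 controls in all and about 9 at the interim (one third of 27). When the control arm is the smaller one, chance runs of early control events push the statistic further than chance runs of reparixin events do. The upper tail, which favours reparixin, is therefore too heavy.

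SAP 7.1.3.1 bases the decision to start phase 3 on the primary analysis alone, even if the sensitivity analyses disagree. The one p-value that decides the next step would not have the error rate stated for it. An interim crossing also stops phase 2 enrolment under SAP 4.5.

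**Working it through.** **1. Reproducing the plan.** The Table 4 p-values correspond to z = 2.797 (interim) and z = 1.977 (final). With half the information at the interim, the correlation between looks is √0.5. Ignoring futility, the bivariate normal gives P(Z₁ > 2.797 or Z₂ > 1.977) = 0.0250. The Table 5 bounds give 0.0248. For power, the drift at 2 versus 5 days (hazard ratio 0.4) is √(46 × 2/9) × ln 2.5 = 2.93. Power is then 0.801 if the futility bound is followed and 0.831 if it is not. The bounds and the stated power are therefore correct in large samples.

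**2. Direction of the skew, by hand.** Take the control share of the risk set as fixed at 1/3. Each event then adds variance 2/9 and third central moment (1/3)(2/3)(1/3) = 2/27 to the control observed-minus-expected total. The skewness is (2D/27)/(2D/9)^1.5, which is 0.147 for D = 23 and 0.104 for D = 46. The first-order tail correction is φ(z) × (skewness/6) × (z² − 1):

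- Interim: 0.00258 + 0.00799 × 0.147/6 × 6.82 = 0.0039.
- Final: 0.02400 + 0.0565 × 0.104/6 × 2.91 = 0.0269.

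This shows only the direction and order of magnitude. It ignores ties and the changing risk-set share.

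**3. Simulation of the phase 2 procedure under no effect.** Inputs from the documents are 32 versus 16 patients, enrolment over two months (61 days), 21-day follow-up, looks at event 23 and at the end, and non-binding futility. The log-rank uses the tie-corrected hypergeometric variance. The following are assumptions:

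- uniform accrual
- exponential times with common median 2, 3 or 5 days
- visits at days 1, 2, 7, 21 and 28, with end of treatment at day 21
- 2:1 blocks of 3 or 6
- 4 sites (the number is not given)

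There were 200,000 trials per cell (SE about 0.0004).

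| Event dating | Overall error (stated: under 0.025) | Interim crossing (nominal 0.00258) |
|---|---|---|
| All at visits | 0.028 | 0.0033–0.0034 |
| Half at visits | 0.032–0.033 | 0.0048–0.0049 |
| All whole-day | 0.033–0.035 | 0.0046–0.0052 |
| Exact times (upper reference only) | 0.036–0.039 | 0.0064–0.0075 |

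Separately written code gave 0.028–0.029 (visit), 0.0315–0.034 (mixed) and 0.032–0.035 (whole-day), with whole-day interim crossings of 0.0044–0.0059. The opposite tail was 0.022–0.025, so the excess lies on the side that favours reparixin. Accrual over 20 days (whole-day dating) or 90 days (visit dating) gave 0.034 and 0.028.

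**4. Phase 3.** With three looks (events 60, 81 and final), 111 patients and medians of 2 and 4 days, 60,000 trials per cell gave 0.031 (whole-day), 0.026–0.028 (all at visits) and 0.033 (exact).

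**5. Re-randomization p-values with unchanged thresholds.** Phase 2 gave 0.0248 (whole-day), 0.0243 (visit) and 0.0256 (exact), SE about 0.0005–0.0008. With 1 or 8 sites the range was 0.0238–0.0251. Phase 3 gave 0.0244–0.0247 (SE 0.0012). A coarser check, with 1,000 unstratified permutations per look, gave 0.022–0.023 in phase 2 (SE 0.0014–0.0017).

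**The case against.** - **Large-sample convention.** No bound is miscalculated, and the stated limit is the usual asymptotic claim. That is true, but the SAP states a limit and compares p-values with it to five decimals. At this size the named test exceeds the limit by 0.003 to 0.010.
- **Phase 2 is only a gate.** SAP 7.1.1.1 calls its result preliminary, and superiority needs both rejections. This stands as a limit on what is at stake. The study-level error is at its highest when the phase 2 effect is large and real and the phase 3 endpoint is null, and it then approaches the phase 3 error of 0.026–0.031. At the planned phase 2 effect, and assuming the two tests are independent, it is about 0.031 × 0.82 = 0.025 (whole-day) or 0.028 × 0.72 = 0.020 (visit-dated). A material excess for the overall claim is not shown.
- **Futility.** SAP 4.5 reads as if stopping follows once superiority is excluded. If the futility bound were always obeyed, the phase 2 error would be about 0.025–0.027 (visit-dated) and 0.029–0.032 (whole-day). That is smaller, but with whole-day dating still above 0.025. Protocol 9.4.5 makes the bound non-binding, so it cannot be credited.
- **Dating mix.** The share of visit-dated events is not in the documents. If it is high, the excess is about 0.003. This stands, and is why a range is given.
- **Phase 3 is provisional.** Its design will be amended, so those figures describe only the present plan.

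**Conclusion.** The concern holds. The phase 2 test as specified has a one-sided type I error of about 0.028 to 0.035, not under 0.025. In relative terms this is 12% to 40% above the limit (0.028/0.025 and 0.035/0.025). The interim bound is crossed in roughly 0.003 to 0.006 of null trials. The range rests on exponential times with medians of 2 to 5 days, uniform accrual, the assumed visit grid, non-binding futility and an unknown share of visit-dated events. No dating scenario brought the error to 0.025 with futility non-binding. The excess is modest, and it concerns the phase 2 gate and, less strongly, the phase 3 test. It should be fixed, because the error statement is wrong for the named test and the remedy is inexpensive.

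**What to change.** For both primary tests, specify that the one-sided log-rank p-value comes from the re-randomization distribution, and keep the Table 4 and Table 5 thresholds. The reference set follows SAP 3.3: "Randomization will be stratified by site to ensure balanced assignment across treatment groups". Regenerate the site-stratified 2:1 permuted-block list at least 100,000 times. At the interim bound the Monte Carlo SE is then √(0.00258 × 0.99742/100,000) = 0.00016.

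The alternative is to calibrate the bounds by simulation under the SAP 9.1 dating rules. With whole-day dating, z would be about 3.00–3.07 at the interim and 2.10–2.13 at the final look, instead of 2.797 and 1.977. Other dating mixes need their own calibration.

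Restate the error and the power in SAP 3.2. The programming is short; the cost is power:

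- Phase 2 at 2 versus 5 days: about 82% to 77% (whole-day), 72% to 70% (all visit-dated), 83% to 77% (exact times).
- Phase 3 at 2 versus 4 days: about 91% to 90% (whole-day).

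The phase 2 figures fall below the stated 80%, so the sponsor must accept the lower power or reconsider the sample size.

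Two related texts need attention, although the finding does not depend on them:

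- Protocol 5.1 states: "Enrollment can be interrupted at any given time for futility or clear superiority reasons of the oral tablet vs IV infusion". Protocol 9.4.5 plans one phase 2 efficacy interim and limits unplanned looks to safety data. The two must be reconciled.
- The amendment required by SAP 4.7 should say whether the 48 phase 2 patients count in the phase 3 test. If they count after a data-driven change under Table 6, hierarchical testing alone does not protect the error. The amendment should then fix a combination test with preset weights, or test only patients randomized after the change. The second option leaves 111 − 48 = 63 patients (about 62 events). Single-look power at hazard ratio 0.5 is Φ(√(62 × 2/9) × ln 2 − 1.96) = 73%, against 93% with 109 events.
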